6.6. Monitoring plan and data management

6.6.1. Data Collection

For each patient, the data collected during the trial will be spread over 3 media:

- an electronic case report form (eCRF) for the investigator,
- a follow-up booklet to be completed by the patient,
- a database dedicated to blind X-ray review campaigns.

All the information required by the protocol must be provided on these media. They must include the data needed to confirm compliance with the protocol and all the data required for statistical analysis, and enable major deviations from the protocol to be identified.

The people responsible for filling in the CRFs must be defined and identified in the center's task delegation table and recorded in the trial's files at each investigating center. They undertake to comply with the rules for completion set out in the specific manual handed out during the set-up visit.

In this trial, no directly identifying information (identity, address, social security number) or sensitive information will be collected.

The health data collected concerns only:

- patient demographics (gender, age),
- relevant history and treatments taken at the time of enrolment,
- data relating to the tooth to be treated: tooth number, pulpal and periapical pathology, number of canals to be treated,
- pre— and post-operative X-ray image(s); these will all be anonymous, distinguishable by the subject's identifier number.

6.6.2. Identification of all source data not contained in the medical file

The following data may be collected directly in the eCRF, without being notified in the source file: data relating to operating techniques.

6.6.3. Right of access to source data and documents

By definition, a source document is any original document or object that can be used to prove the existence or accuracy of data, such as patient medical records.

The investigator will make the documents and individual data, which is strictly necessary for the monitoring, quality control and audit of the trial, available to persons with access to these documents in accordance with current applicable legislative and regulatory provisions (Articles L.1121-3 and R.5121-13 of the Public Health Code and Annex XV of Regulation (EU) 2017/745 on medical devices). The medical data relating to each subject collected for this trial and coded will only be transmitted to the Sponsor or any person duly authorized by them, and, where applicable, to authorized health authorities, under conditions guaranteeing confidentiality.

In accordance with applicable legislative provisions (Articles L.1121-3 and R.5121-13 of the Public Health Code and Annex XV of Regulation (EU) 2017/745 on medical devices), persons with direct access to the source data will take all necessary precautions to ensure the confidentiality of information relating to the trial, to the persons who take part in it and in particular with regard to their identity and to the results obtained.

The Sponsor and regulatory authorities may request direct access to the medical file in order to verify the clinical trial's procedures and/or data, without breaching confidentiality and within the limits authorized by law and by the regulations.

The data collected during the study may be processed electronically, in compliance with the General Data Protection Regulation (GDPR, EU Regulation 2016/679) and the requirements of the CNIL, in accordance with the reference methodology MR-001 (deliberation no. 2016-262 dated 21 July 2016 amending the reference methodology for the processing of personal data carried out in the context of biomedical research; Declaration of compliance provided in Appendix 4).

To ensure the confidentiality of the personal data relating to subjects participating in the trial, a 5-character alphanumeric code will be assigned to each subject (see below).

Persons authorized to access medical records are bound by professional secrecy.

6.6.4. Data encoding:

Identifier of trial patient:

By signing this protocol, the investigator and their collaborators undertake to keep confidential the identities of the subjects taking part in this clinical trial.

The observation booklet, the follow-up booklet and all other source documents attached to the CRF (including X-ray images) will be pseudonymized: each included patient will receive a four-digit identification code and a letter in the following format (NNN-CN). This alphanumeric code will be the only information to appear in the case report book and will enable the CRF to be linked to the patient *at a later date*.

NNN-CN

N: center number (from 1 to 7)

NN: center enrolment number (in chronological order of enrolment)

C: treatment arm: N = PA1704; R = BioRoot™ RCS

N: stratum number: 1 = Initial Endodontic Treatment (ET); 2 = Re-treatment (ER).

Examples:

Code of 1st patient enrolled at center 4 with indication of ET and treated with PA1704: 401-N1

Code of 12th patient enrolled at center 2 with indication of ER and treated with BioRoot™ RCS = 212-R2

The list of matching identification numbers and patient identities will be managed and kept by the investigator in paper format and archived with the trial documents specific to his/her center **only** at his/her premises.

Encoding of adverse events and device defects:

The IMDRF terminology (appendices A to G) will be used to encode adverse events related to medical devices and device defects (see details in chapter 14 on vigilance).

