6.1. General points and methodology

✓ Methodology — trial design

Prospective, multicenter, randomized, controlled, open-label study, with blind evaluation of the primary criterion and several secondary criteria (PROBE design).

Parallel group design (1:1):

- The arm receiving the device under investigation: PA1704
- The arm receiving the comparator medical device: BioRoot™ RCS.

✓ Measures to reduce or avoid bias.

Randomization and stratification:

Before the trial is set up, the CRO's biostatistician will computer-generate a block randomization list stratified by clinical indication (initial endodontic treatment (ET) versus re-treatment (ER)). The randomization system will be integrated directly into the electronic CRF.

Randomization will be carried out by the electronic CRF once the eligibility criteria have been checked, the clinical indication (ET or ER) has been determined and all this information has been recorded in the specific module by the investigator.

It should be noted that the proportion of ERs will be 30% of the overall sample, which is close to the rate reported in a French Health Insurance survey (Masson 2002). The rate of ER may vary between sites: some investigators, because of their specialty in endodontics, will include a majority of patients with an indication for re-treatment, whereas GP investigators will probably have more indications for first-line treatment.

Blind:

Investigators and patients will not be blind to the medical device allocated due to the different ways in which the 2 products are presented and used. On the other hand, two independent qualified assessors (previously calibrated under the supervision of the study coordinator) will conduct the blind, centralized review of the retro-alveolar X-rays taken at TO (reference radiograph obtained immediately post-operatively), 6 months, 12 months, 24 months, 3.5 years and 5 years (Refer to Section "Equipment to be used to evaluate clinical trial variables and arrangements for monitoring maintenance and calibration." section of this chapter); they will be blinded to centre, patient, indication (initial or repeat endodontic treatment), and treatment arm; the files will first be anonymized by the CRO.

✓ Outcome measures

Primary criterion (composite criterion):

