The Per Protocol (PP) population is the entire mITT population that perfectly complied with the protocol. Thus, subjects with major protocol violations, including major false inclusions (see below), and subjects for whom the primary criterion was not available, will be excluded from the PP population.

Major enrolment breaches include:

- No signed consent,
- Enrolment of a vulnerable subject,
- Enrolment of a patient with a contraindication to endodontic treatment or a known contraindication to the use of BioRoot™ RCS or PA1704 filling material,

Major deviations from the protocol include:

- Error in allocating the medical device,
- Failure to comply with the procedure for using the medical device,
- · Coronal restoration procedure contraindicated or insufficient,
- · Lost contact,
- No performance data,

Particular care will be taken to describe any deviations from the protocol.

All major deviations will be validated by the coordinating investigator, ideally during clinical implementation and monitoring visits, or at the latest at the time of data review; the evaluation will be carried out blind to the data relating to whichever medical device was allocated and data collected after randomization.

It should be noted that non-compliance with the schedule of visits scheduled at 6, 12 and 24 months (with a tolerance of \pm 1 month) will be considered a minor deviation from the protocol; the same applies in the case of a coronal restoration carried out after more than 45 days.

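### The patient code spells out treatment arm and stratum, and no masking step is described for the device-blind review that fixes the mITT and per-protocol sets

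*Combined protocol and SAP*

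**What the plan says.** Section 6.6.4 (Data encoding) defines the code NNN-CN. The first digit is the centre and the next two are the order of enrolment there. The letter is the arm: "C: treatment arm: N = PA1704; R = BioRoot" RCS. The last digit is the indication: "N: stratum number: 1 = Initial Endodontic Treatment (ET); 2 = Re-treatment (ER"). The section's own example is "Code of 1st patient enrolled at center 4 with indication of ET and treated with PA1704: 401-N1". The code goes on the observation booklet and the follow-up booklet, and "all other source documents attached to the CRF (including X-ray images) will be pseudonymized" with it. Section 6.6.1 says of the images that "these will all be anonymous, distinguishable by the subject's identifier number".

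Two blinds are promised.

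- **Image reading** (section 6.1, Blind). Of the two independent readers it says "they will be blinded to centre, patient, indication (initial or repeat endodontic treatment), and treatment arm", and the CRO anonymizes the files first. Section 6.1 also says that the readers work from anonymized images, and section 6.6.1 gives the reading campaigns a database of their own.
- **Eligibility and deviation review** (section 7.6). Breaches of eligibility are to be judged without knowledge of the device or of post-randomization data. For major deviations, "the evaluation will be carried out blind to the data relating to whichever medical device was allocated" and to data collected after randomization. The coordinating investigator validates major deviations, preferably during monitoring visits and at the latest at data review.

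Section 7.7.4 makes the per-protocol analysis the main one, with mITT as its complement.

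**The concern.** In an open-label trial with blinded endpoint evaluation, the patient number should carry no information that a blinded person must not have. Here it carries the arm in plain letters. The risk is greatest in the review that fixes the analysis sets. Some of the listed major deviations call for judgement, such as whether the device procedure was followed or whether the coronal restoration was adequate. Each decision removes a patient from the primary analysis or keeps the patient in it. If the person deciding can see the arm, exclusions can differ between arms for reasons unrelated to conduct, and in a non-inferiority trial the direction of the resulting bias is not predictable. Section 7.5 also brings the sponsor and the CRO's biostatistician together before each analysis to categorize deviations, so several people may work from coded records.

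**Working it through.** This is mainly a comparison of provisions.

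**1. What the code reveals, against what must be hidden**

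| Part of code (6.6.4) | Meaning | Hidden from image readers (6.1)? | Hidden from eligibility and deviation review (7.6)? |
|---|---|---|---|
| First digit | Centre | Yes | Not required |
| Next two digits | Patient sequence | Yes (patient) | Not required |
| Letter N or R | Arm | Yes | Yes |
| Last digit 1 or 2 | Indication stratum | Yes | Not required |

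The code discloses all four items withheld from the readers and the one allocation item withheld in section 7.6.

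**2. Whether a step removes the code**

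- *Image reading:* yes. Section 6.1 has the CRO anonymize the files and lists the same four items as masked. What the step does is not specified. Section 6.1 separately calls for anonymization before images are uploaded to the eCRF, section 6.6.1 calls images anonymous while telling them apart by the code, and section 6.6.4 calls them pseudonymized under the code. In this document, then, an anonymous image can still carry the arm letter. Nothing says that the CRO substitutes a neutral reading number.
- *Eligibility and deviation review:* none is described. Section 7.6 states the blind but not how it is kept, and sections 7.5, 7.7 and 8 add nothing on it.

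**3. Whether a neutral code would be enough for section 7.6**

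Not entirely. A listed major deviation is an error in allocating the device, which cannot be judged without knowing the device. Failure to follow the device procedure can also reveal it, because section 6.5.1 (Table 5) gives different steps for a syringe paste and for a powder and liquid mix. These need a separate route.

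**4. Effect on the planned figures**

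Inputs from sections 7.2 and 7.3: 90% efficacy in both arms, margin 13 points, one-sided alpha 5%, power 80%.

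n = (1.645 + 0.842)² × 2 × 0.90 × 0.10 / 0.13² = 6.18 × 0.18 / 0.0169 = 65.9, rounded up to 66 per group. This is the plan's figure. With 20% added, 66 × 1.20 = 79.2, rounded up to 80 per group, also the plan's figure. Neither calculation involves the code.

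**5. How much one decision could matter**

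Take 66 per arm and a one-sided 95% Wald limit, with counts chosen close to the margin:

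- 57/66 v 60/66: difference -4.5 points, SE 5.51, limit -4.5 - 1.645 × 5.51 = -13.6. Non-inferiority is not shown.
- 58/66 v 60/66: difference -3.0 points, SE 5.35, limit -11.8. Non-inferiority is shown.

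This is ordinary fragility of a binary endpoint near its margin. It does not estimate how often the arm would be seen or whether seeing it would change a decision.

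**The case against.** A reader might infer that the code defeats the blinding of the image reading. The document does not support that. It masks exactly the items that the code would show, has the CRO anonymize the files, and provides a separate reading database. At 3.5 and 5 years the readers know the arm by design, because only PA1704 patients are followed. What stands is a gap in wording about what the anonymization removes.

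A reader might also infer that deviations are judged on listings that show the arm. The document describes no such listings. It requires the blind and is silent on the method, so a masking procedure may exist elsewhere, for instance in the separate statistical analysis plan announced in section 7.7.

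Two other uses of coded material may look like breaches but are not. The coordinator's advice on X-rays before retreatment (section 6.5.2) is nowhere said to be blind. The pain booklet is completed by patients who already know their device.

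Finally, image masking is not the trial's only protection against bias: allocation is randomized and stratified through the eCRF, and there are two calibrated readers. The clinical half of the primary criterion is open-label in any case. All of this stands. It narrows the point but does not answer the missing masking step in section 7.6.

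**Conclusion.** The point holds in a limited form. The code discloses centre, arm and stratum on documents and images. The review that settles the mITT and per-protocol sets must be blind to device, and no step is described that would make it so for a person who sees the code. For image reading a safeguard is in the plan, but its content is left open. The possible bias has no number: the document gives no basis for estimating how often the arm would be seen or acted on, and the limits of -13.6 and -11.8 points only illustrate fragility near the margin. The conclusion assumes that records used in the eligibility and deviation review carry the patient code, as section 6.6.4 implies for case report and source documents, and that no masking procedure exists outside this document. If one exists, stating it would meet most of the point. The matter should be corrected; it does not invalidate the design.

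**What to change.** - In section 6.6.4, replace the code with a patient number made of centre and sequence only. Hold arm and stratum in a restricted eCRF field.
- In section 6.1, state that the CRO gives each image a random reading number and removes the patient code from the image and its file name before reading. Use one term consistently in sections 6.1, 6.6.1 and 6.6.4 for images that still carry a code.
- In section 7.6, state that the eligibility and deviation review runs on records without arm. Send allocation errors, and other deviations that reveal the device, through a separate documented route.

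The cost is a change to the eCRF and label specification. If patients are already coded, the CRO can re-key image names and review records once and leave the site codes as they are, so the paper identity lists at the centres need not change. Sample size, alpha and power stay the same.

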6.6.5. Data quality & monitoring

Data monitoring will be carried out by the CRO's CRAs, in accordance with Good Clinical Practice aimed at guaranteeing the quality of the trial. As the OPTIFILL trial is a category 1 RIPH involving a class IIa medical device that is not CE marked, the level of control will be high.

The CRAs will carry out regular remote monitoring *via* the ENNOV Clinical software application to track recruitment and check the integrity of the data entered into the eCRF. Requests for corrections or clarification of data will be sent to the investigator electronically.

In addition, the CRO's CRAs will regularly visit the investigating centres; 6 site visits are planned: 1 visit soon after the first enrolments, then a site visit after each follow-up visit provided for in the protocol, for up to 5 years of patient follow-up. The CRAs will check and verify consent forms, the consistency of critical data (PEC clinical criteria, AEs, patient record data, device defects) and equipment.

Visits will be organized after making an appointment with the investigator. The CRA must be able to consult:

- Consent forms,
- Observation and monitoring records,
- Patient source files (paper and/or electronic format),
- Medical devices made available (PA1704 and Bioroot™ RCS)
- Investigator file provided by the CRO.

7. Statistical considerations

7.1. Software used:

 Creation of the input template for the electronic CRF and patient record, database media: Ennov Clinical version 8.0,

Statistical analysis: JMP[®] version 15.0.0 or later (SAS Institute) on Windows 10 Pro.

7.2. Size of sample:

Based on the assumption that there is no difference in efficacy at 2 years between the 2 filling materials (PA1704 and BioRoot™ RCS) and that the expected efficacy rate of BioRoot™ RCS after initial and repeated endodontic treatment is 90% (Zavattini et al., 2019; Chybowski et al., 2018, Bardini et al., 2016), we calculate that a minimum of 66 subjects per group must be enrolled **to show non-inferiority of PA1704 over BioRoot™ RCS** with a confidence interval of 80%, a unilateral alpha risk of 5% and a 13% difference in efficacy tolerance between the 2 products (Ng 2007; Ng 2008; Eyuboglu 2016). By enrolling an additional 20% of patients in order to take into account those lost to or withdrawn from the trial, **the number of patients who must be included is 80 in each group, or 160 patients in total.**

Patients will be enrolled either due to an indication for initial endodontic treatment or due to indication for repeat treatment; the proportion of repeat treatments will be 30%.

7.3. Degree of significance and power of the clinical trial

The main analysis will be carried out using a one-tailed statistical test with a significance threshold α set at 5%. The clinical trial is designed to ensure 80% power for the main analysis test. Secondary analyses will be carried out using two-tailed statistical tests with a significance threshold α set at 5%.

7.4. Expected drop-out rates

The study includes a 24-month follow-up for patients in the BioRoot RCS arm, and a 5-year follow-up for patients in the PA1704 arm, which may mean that some patients will withdraw or be dropped from the study. These patients will not be replaced. The calculation of the number of subjects to be enrolled allowed for a 20% increase in this number, in order to anticipate the drop-out rate at 2 years.

7.5. Procedures for taking all data into account:

Data review and database freezing: Before each statistical analysis (intermediate and final), a data review meeting will be held, attended by *at least* the sponsor and the CRO's biostatistician in charge of the statistical analysis. This will enable deviations from the protocol to be identified and categorized, so that samples of patients can be evaluated for statistical analysis. This will provide an opportunity to identify factors not initially considered that could influence the trial results and which would be worth taking into account in the analysis. At the end of the last data review meeting, the clinical database will be frozen.

Once the clinical database has been frozen, statistical analyses will be carried out by the CRO in accordance with the trial's Statistical Analysis Plan.

7.6. Definition of analysis populations:

The Tolerance population is the entire population treated with the investigational MD or the comparator MD. Patients will be analyzed according to the medical device they actually received (if a patient is randomized to one arm but receives the medical device from the other arm (allocation error), they will be analyzed according to the medical device they actually received).

The modified ITT (mITT) population is the set of patients included in the clinical trial, meeting the major eligibility criteria (see below), having been treated with one of the MDs, and for whom at least one set of performance data is available (efficacy at 6 months, 12 months or 24 months based on clinical and radiological criteria). Evaluation of breaches of the eligibility criteria will be carried out blind to whichever medical device was allocated and to post-randomization data. Patients will be analyzed according to the intention-to-treat principle, i.e. according to the medical device for which they have been randomized.

The Per Protocol (PP) population is the entire mITT population that perfectly complied with the protocol. Thus, subjects with major protocol violations, including major false inclusions (see below), and subjects for whom the primary criterion was not available, will be excluded from the PP population.

Major enrolment breaches include:

- No signed consent,
- Enrolment of a vulnerable subject,
- Enrolment of a patient with a contraindication to endodontic treatment or a known contraindication to the use of BioRoot™ RCS or PA1704 filling material,

Major deviations from the protocol include:

- Error in allocating the medical device,
- Failure to comply with the procedure for using the medical device,
- · Coronal restoration procedure contraindicated or insufficient,
- · Lost contact,
- No performance data,

Particular care will be taken to describe any deviations from the protocol.

All major deviations will be validated by the coordinating investigator, ideally during clinical implementation and monitoring visits, or at the latest at the time of data review; the evaluation will be carried out blind to the data relating to whichever medical device was allocated and data collected after randomization.

It should be noted that non-compliance with the schedule of visits scheduled at 6, 12 and 24 months (with a tolerance of \pm 1 month) will be considered a minor deviation from the protocol; the same applies in the case of a coronal restoration carried out after more than 45 days.

